### **12.2 Disease Parameters**

Measurable Disease: Measurable lesions are defined as those that can be accurately measured in at least one dimension (longest diameter for non-nodal lesions and short axis for nodal lesions to be recorded) as  $\geq 20$  mm by chest x-ray, as  $\geq 10$  mm with CT scan, or  $\geq 10$  mm with calipers by clinical exam. All tumor measurements must be recorded in millimeters (or decimal fractions of centimeters). Tumor lesions that are situated in a previously irradiated area will not be considered measurable.

Malignant lymph nodes: To be considered pathologically enlarged and measurable, a lymph node must be  $\geq 15$  mm in short axis when assessed by CT scan (CT scan slice thickness recommended to be no greater than 5 mm). At baseline and in followup, only the short axis will be measured and followed.

Non-measurable disease: All other lesions (or sites of disease), including small lesions (longest diameter  $< 10$  mm or pathological lymph nodes with  $\geq 10$  to  $< 15$  mm short axis) are considered

non-measureable disease. Bone lesions, leptomeningeal disease, ascites, pleural/pericardial effusions, lymphangitis cutis/pulmonitis, inflammatory breast disease, and abdominal masses (not followed by CT or MRI) are considered as non-measureable.

**Note:** Cystic lesions that meet the criteria for radiographically defined simple cysts should not be considered as malignant lesions (neither measurable nor non-measurable) since they are, by definition, simple cysts.

‘Cystic lesions’ thought to represent cystic metastases can be considered as measureable lesions if they meet the definition of measurability described above. However, if non-cystic lesions are present in the same patient, these are preferred for selection as target lesions.

**Target lesions:** All measureable lesions up to a maximum of 2 lesions per organ and 5 lesions in total, representative of all involved organs, should be identified as **target lesions** and recorded and measured at baseline. Target lesions should be selected on the basis of their size (lesions with the longest diameter), be representative of all involved organs, but in addition should be those that lend themselves to reproducible repeated measurements. It may be the case that, on occasion, the largest lesion does not lend itself to reproducible measurement in which circumstance, the next largest lesion which can be measured reproducibly should be selected. A sum of the diameters (longest for non-nodal lesions, short axis for nodal lesion) for all target lesions will be calculated and reported as the baseline sum diameters. If lymph nodes are to be included in the sum, then only the short axis is added into the sum. The baseline sum diameters will be used as reference to further characterize any objective tumor regression in the measurable dimension of the disease.

**Non-target lesions:** All other lesions (or sites of disease) including any measureable lesions over and above the 5 target lesions should be identified as **non-target lesions** and should also be recorded at baseline. Measurement of these lesions are not required, but the presence, absence, or in rare cases unequivocal progression of each should be noted throughout followup.

### 12.3 Methods for Evaluation of Measureable Disease

All measurements should be taken and recorded in metric notation using a ruler or calipers. All baseline evaluations should be performed as closely as possible to the beginning of treatment and never more than 4 weeks before the beginning of treatment.

The same method of assessment and the same technique should be used to characterize each identified and reported lesion at baseline and during followup. Imaging-based evaluation is preferred to evaluation by clinical examination unless the lesion(s) being followed cannot be imaged, but are assessable by clinical exam.

**Clinical lesions:** Clinical lesions will only be considered measureable when they are superficial (e.g. skin nodules and palpable lymph nodes) and  $\geq 10$  mm diameter as assessed using calipers (e.g. skin nodules). In the case of skin lesions, documentation by color photography including a ruler to estimate the size of the lesion is recommended.

**Chest x-ray:** Lesions on chest x-ray are acceptable as measureable lesions when they are clearly

defined and surrounded by aerated lung. However, CT is preferable.

**Conventional CT and MRI:** This guideline has defined measurability of lesion on CT scan based on the assumption that CT slice thickness is 5 mm or less. If CT scans have slice thickness greater than 5 mm, the minimum size for a measureable lesion should be twice the slice thickness. MRI is also acceptable in certain situations (e.g. for body scans).

Use of MRI remains a complex issue. MRI has excellent contrast, spatial, and temporal resolution; however, there are many image acquisition variables involved in MRI which greatly impact image quality, lesion conspicuity, and measurement. Furthermore, the availability of MRI is variable globally. As with CT, if an MRI is performed, the technical specifications of the scanning sequences used should be optimized for the evaluation of the type and site of disease. Furthermore, as with CT, the modality used at followup should be the same as was used at baseline and the lesions should be measured/assessed on the same pulse sequence. It is beyond the scope of the RECIST guidelines to prescribe specific MRI pulse sequence parameters for all scanners, body parts, and diseases. Ideally, the same type of scanner should be used and the image acquisition protocol should be followed as closely as possible to prior scans. Body scans should be performed with breath-holding techniques, if possible.

**PET-CT:** At present, the low dose or attenuation correction CT portion of a combined PET-CT is not always of optimal diagnostic CT quality for use with RECIST measurements. However, if the site can document that the CT performed as part of a PET-CT is of identical diagnostic quality to a diagnostic CT (with IV and oral contrast), then the CT portion of the PET-CT can be used for RECIST measurements and can be used interchangeably with conventional CT in accurately measuring cancer lesions over time. Note, however, that the PET portion of the CT introduces additional data, which may bias an investigator if it is not routine or serially performed. *PET may not be used for making determinations regarding response to treatment.*

**Ultrasound:** Ultrasound is not useful in assessment of lesion size and should not be used as a method of measurement. Ultrasound examinations cannot be reproduced in their entirety for independent review at a later date and because they are operator dependent, it cannot be guaranteed that the same technique and measurements will be taken from one assessment to the next. If new lesions are identified by ultrasound in the course of the study, confirmation by CT or MRI is advised. If there is concern about radiation exposure at CT, MRI may be used instead of CT in selected instances.

**Endoscopy, Laparoscopy:** The utilization of these techniques for objective tumor evaluation is not advised. However, such techniques may be useful to confirm complete pathologic response when biopsies are obtained or to determine relapse in trials where recurrence following complete response (CR) or surgical resection is an endpoint.

**Tumor Markers:** Tumor markers alone cannot be used to assess response. If markers are initially above the upper normal limit, they must normalize for a patient to be considered in complete clinical response.

**Cytology, Histology:** These techniques can be used to differentiate between partial responses

(PR) and complete responses (CR) in rare cases (e.g. residual lesions in tumor types, such as germ cell tumors where known residual benign tumors can remain).

The cytological confirmation of the neoplastic origin of any effusion that appears or worsens during treatment when the measurable tumor has met criteria for response or stable disease is mandatory to differentiate between response or stable disease (an effusion may be a side effect of the treatment) and progressive disease.

## 12.4 Response Criteria

### Evaluation of Target Lesions

Response	Evaluation of Target Lesions
Complete Response (CR)	Disappearance of all target lesions. Any pathologic lymph nodes (whether target or non-target) must have reduction in short axis to < 10 mm.
Partial Response (PR)	At least a 30% decrease in the sum of diameters of target lesions, taking as reference the baseline sum of diameters.
Progressive Disease (PD)	At least a 20% increase in the sum of diameters of target lesions, taking as reference the smallest sum on study (this includes the baseline sum if that is the smallest on study). In addition to the relative increase of 20%, the sum must also demonstrate an absolute increase of at least 5 mm. Note: the appearance of one or more new lesions is also considered progression.
Stable Disease (SD)	Neither sufficient shrinkage to qualify for PR nor sufficient increase to qualify for PD, taking as reference the smallest sum of diameters while on study.

### Evaluation of Non-Target lesions

Response	Evaluation of Non-Target Lesions
Complete Response (CR)	Disappearance of all non-target lesions and normalization of tumor marker level. All lymph nodes must be non-pathological in size (< 10 mm short axis). Note: If tumor markers are initially above the upper normal limit, they must normalize for a patient to be considered in complete clinical response.

Non-CR/Non-PD [Incomplete response/Stable Disease (SD)]	Persistence of one or more non-target lesion(s) and/or maintenance of tumor marker level above the normal limits.
Progressive Disease (PD)	
Appearance of one or more new lesions and/or unequivocal progression of existing non-target lesions. Unequivocal progression should not normally trump target lesion status. It must be representative of overall disease status change, not a single lesion increase.
 
Although a clear progression of 'non-target' lesions only is exceptional, the opinion of the treating physician should prevail in such circumstances, and the progression status should be confirmed at a later time by the review panel (or PI).

### Evaluation of Best Overall Response

The best overall response is the best response recorded from the start of the treatment until disease progression/recurrence (taking as reference for progressive disease the smallest measurements recorded since the treatment started). The patient's best response assignment will depend on the achievement of both measurement and confirmation criteria.

### For Patients with Measureable Disease (e.g. Target Disease)

Target Lesions	Non-Target Lesions	New Lesions*	Best Overall Response	Remarks
CR	CR	No	CR	
CR	Non-CR/Non-PD***	No	PR	
CR	Not evaluated	No	PR	
PR	Non-PD***/not evaluated	No	PR	
SD	Non-PD***/not evaluated	No	SD	Documented at least once $\geq 8$ wks. from study entry
PD	Any	Yes or No	PD	No prior SD, PR or CR
Any	PD**	Yes or No	PD***	
Any	Any	Yes	PD	

\* See RECIST 1.1 manuscript for further details on what is evidence of a new lesion.

\*\* In exceptional circumstances, unequivocal progression in non-target lesions may be accepted as disease progression.

\*\*\*PD in non-target lesions should not normally trump target lesion status. It must be representative of overall disease status change, not a single lesion increase. Please refer to the Evaluation of Non-Target Lesions – Progressive Disease (Section 12.2) for further

explanation.

**NOTE:** Patients with a global deterioration of health status requiring discontinuation of treatment without objective evidence of disease progression at that time should be reported as “*symptomatic deterioration*.” Every effort should be made to document the objective progression even after discontinuation of treatment.

Duration of overall response: The duration of overall response is measured from the time measurement criteria are met for CR or PR (whichever is first recorded) until the first date that recurrent or progressive disease is objectively documented (taking as reference for progressive disease the smallest measurements recorded since the treatment started). The duration of overall CR is measured from the time measurement criteria are first met for CR until the first date that progressive disease is objectively documented.

Duration of stable disease: Stable disease is measured from the start of the treatment until the criteria for progression are met, taking as reference the smallest measurements recorded since the treatment started, including the baseline measurements.

## **12.5 Progression Free Survival**

Progression-free survival (PFS) is defined as the duration of time from start of treatment to time of progression or death, whichever occurs first.

## **13.0 DATA REPORTING / REGULATORY CONSIDERATIONS**

Adverse event lists, guidelines, and instructions for AE reporting can be found in Section 8.0 (Adverse Events: List and Reporting Requirements).

### **13.1 Data Reporting**

The OnCore™ Database will be utilized, as required by the Case Comprehensive Cancer Center, to provide data collection for both accrual entry and trial data management. OnCore™ is a Clinical Trials Management System housed on secure servers maintained at Case Western Reserve University. OnCore™. Access to data through OnCore™ is restricted by user accounts and assigned roles. Once logged into the OnCore™ system with a user ID and password, OnCore™ defines roles for each user which limits access to appropriate data. User information and password can be obtained by contacting the OnCore™ Administrator at [contact].

OnCore™ is designed with the capability for study setup, activation, tracking, reporting, data monitoring and review, and eligibility verification. This study will utilize electronic Case Report Form completion in the OnCore™ database. A calendar of events and required forms are available in OnCore™.

### **13.2 Regulatory Considerations**

The study will be conducted in compliance with ICH guidelines and with all applicable federal (including 21 CFR parts 56 & 50), state or local laws.

### **13.2.1 Written Informed consent**

Provision of written informed consent must be obtained prior to any study-related procedures. The Principal Investigator will ensure that the patient is given full and adequate oral and written information about the nature, purpose, possible risks and benefits of the study as well as the patient's financial responsibility. Patients must also be notified that they are free to discontinue from the study at any time. The patient should be given the opportunity to ask questions and be allowed time to consider the information provided.

The original, signed written Informed Consent Form must be kept with the Research Chart in conformance with the institution's standard operating procedures. A copy of the signed written Informed Consent Form must be given to the patient. Additionally, documentation of the consenting process should be located in the research chart.

### **13.2.2 Patient Data Protection**

In accordance with the Health Information Portability and Accountability Act (HIPAA), a patient must sign an authorization to release medical information to the sponsor and/or allow the sponsor, a regulatory authority, or Institutional Review Board access to patient's medical information that includes all hospital records relevant to the study, including patients' medical history.

### **13.2.3 Retention of records**

The Principal Investigator of The Case Comprehensive Cancer Center supervises the retention of all documentation of adverse events, records of study drug receipt and dispensation, and all IRB correspondence for as long as needed to comply with local, national and international regulations. No records will be destroyed until the Principal Investigator confirms destruction is permitted.

### **13.2.4 Audits and inspections**

Authorized representatives of the sponsor, sponsor's collaborators, a regulatory authority, an Independent Ethics Committee (IEC) or an Institutional Review Board (IRB) may visit the site to perform audits or inspections, including source data verification. The purpose of an audit or inspection is to systematically and independently examine all study-related activities and documents to determine whether these activities were conducted, and data were recorded, analysed, and accurately reported according to the protocol, Good Clinical Practice (GCP), guidelines of the International Conference on Harmonization (ICH), and any applicable regulatory requirements. For multi-center studies, participating sites must inform the sponsor-investigator of pending audits.

## **14.0 STATISTICAL CONSIDERATIONS**

### **14.1 Study Design/Endpoints**

#### **14.1.1 Definition of Primary Endpoint**

Phase I: Safety, tolerability and recommended phase II dose (RP2D) of combination therapy with CB-839 and capecitabine chemotherapy in patients with no remaining treatment options or patients for whom single agent capecitabine is an acceptable therapy.

Phase II: : Progression free survival (PFS) on combination CB-839 and capecitabine as determined by clinical assessment and RECIST criteria in patients with metastatic PIK3CA mutant colorectal cancer who are refractory to fluoropyrimidine based therapy. Progression free survival is defined as the time from randomization to documented progression or death without progression.

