### **CB-839 and Capecitabine, Cycle 3, sometime between days 15-21 of treatment cycle**

- CT of the chest, abdomen and pelvis for restaging evaluation

**Subsequent CT imaging of the chest, abdomen and pelvis should be performed on an every 9 week basis +/- one week for as long as patient is receiving study treatment**

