## 11.4 Calendar—Phase II Component

Study Days	Pre-Study a	Pre-treatment	CB-839 and cape, C1D1 b	CB-839 and cape, C1D8	CB-839 and cape, C1D15	Cycle 2 and beyond, Day 1	Cycle 3, Day 14-21	Every 9 weeks	30 Day Follow-Up
REQUIRED ASSESSMENTS									
Informed Consent	X								
Demographics	X								
Medical History	X								
Height	X								
Weight	X		X			X			X
Vitals	X		X			X			X
Physical Examination	X		X			X			X
Concomitant Med Assessment	X		X			X			
ECOG PS	X		X			X			X
Symptom/Adverse Event Assessment	X		X	X	X	X			X
CBC with diff d	X		X	X	X	X			X
Serum comprehensive panel d	X		X	X	X	X			X
CEA (carcinoembryonic antigen) blood test	X					X			
Pregnancy test (if applicable)	X								
DISEASE ASSESSMENT									
Tumor measurements		Tumor assessments are performed at baseline and every 9 weeks. Documentation (radiologic) must be provided for patient removed from study for progressive disease.							
CT chest, abdomen and pelvis	X						X	X g	
MISC ITEMS									
Tumor biopsy		X c			X e				
TREATMENT									
CB-839			X h			X			
Capecitabine			X h			X			
CORRELATIVE STUDIES									
Pharmacodynamic studies		X c			X c				
Pharmacokinetics (CB-839)					X f				

a All evaluations must be completed  $\leq$  21 days prior to administration of protocol therapy.

b Cycle 1, Day 1 assessments do not need to be repeated if done within 7 days of initiation of treatment.

c Tumor biopsy may be done up to 14 days prior to initiation of treatment. Please allow 28 days washout from prior systemic therapy prior to pre-treatment biopsy. Platelet glutaminase assay should be drawn the same day as performance of the tissue biopsy. Glutaminase activity will only be assessed on the post-treatment blood and tissue specimens.

d CBC with differential and comprehensive panel for day 1 of the treatment cycle may be drawn up to 24 hours prior to treatment. Serum comprehensive panel should include sodium, potassium, chloride, bicarbonate, BUN, creatinine, glucose, AST, ALT, alk phos, total protein, albumin, total bilirubin, direct bilirubin, magnesium and phosphorus.

e Post-treatment tissue biopsy may be performed day 10-15. Platelet glutaminase assay should be drawn the same day as performance of the tissue biopsy.

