## **12.0 MEASUREMENT OF EFFECT**

Although response is not the primary endpoint of the phase I portion of this trial, patients will be assessed by standard criteria. Response rate is the primary endpoint for the phase II portion of the trial. For the purposes of this study, patients should be re-evaluated every 9 weeks in addition to undergoing a baseline scan.

Response and progression will be evaluated in this study using the new international criteria proposed by the revised Response Evaluation Criteria in Solid Tumors (RECIST) guideline (version 1.1) (23). Changes in the largest diameter (unidimensional measurement) of the tumor lesions and the shortest diameter in the case of malignant lymph nodes are used in the RECIST criteria.

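### The plan does not say how clinical progression without scan evidence enters the Phase II 6-month endpoint; dropping or replacing such patients would bias the rate upward

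*Combined protocol and SAP*

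**What the plan says.** Five parts of the combined protocol and SAP bear on what counts as progression in Phase II.

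- **14.1.1** makes PFS the primary endpoint, "as determined by clinical assessment and RECIST criteria in patients with metastatic PIK3CA mutant colorectal cancer". It runs it as the "time from randomization to documented progression or death without progression". It does not say whether a clinical judgement of progression is enough on its own.
- **12.0** names RECIST 1.1 as the standard for both response and progression. **12.5** defines PFS as "the duration of time from start of treatment to time of progression or death, whichever occurs first" and gives no criterion for progression.
- **12.4** deals with patients whose health declines so that treatment must stop. Those "without objective evidence of disease progression at that time should be reported as" symptomatic deterioration, a category separate from progressive disease. It adds: "Every effort should be made to document the objective progression even after discontinuation of treatment".
- **11.4** (Phase II calendar) states: "Documentation (radiologic) must be provided for patient removed from study for progressive disease". **11.2.2** schedules CT every 9 weeks "for as long as patient is receiving study treatment". The 3-monthly follow-up after discontinuation in 6.7 specifies no imaging.
- **14.2** sets the 6-month PFS rate at 18% (null) against 36% (target). It counts a patient as a success if disease is stable or better at that time. It gives no rule for a patient without a 6-month assessment.

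Separately, **3.3.2** replaces any Phase II patient who takes less than 75% of the planned doses of each agent before the 9-week assessment. It makes no exception for patients who stopped because of clinical decline.

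**The concern.** Take a patient who stops in week 7 because of clinical decline, with no scan showing progression. Scheduled imaging ends with treatment, so there may never be an objective progression date or a 6-month scan. The plan leaves at least four treatments of this patient open: a PFS event, a censored observation, a non-success in the 6-month count, or a patient replaced under 3.3.2.

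These choices are not equivalent. The Phase II decision is a single-arm count against a fixed 18%, so no control arm absorbs a change in how failures are classified. Censoring patients at clinical decline is informative, and removing them takes failures out of the sample. Either one raises the apparent 6-month rate. Because the rule is not fixed in advance, the choice could be made after the outcomes are known.

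**Working it through.** **Step 1: reproduce the stated design.** From 14.2: p0 = 0.18, p1 = 0.36, n1 = 18, N = 40, significance level 0.05, power 80%, early-stopping probability 0.589. From 14.5: Simon two-stage. The final rejection boundary is not stated.

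For a design that stops at r1 or fewer of 18 and declares success at r + 1 or more of 40:

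P(early stop) = P(X1 ≤ r1), with X1 ~ Bin(18, p)

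P(success) = Σ over x > r1 of P(X1 = x) · P(X2 ≥ r + 1 − x), with X2 ~ Bin(22, p)

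- r1 = 3, r = 11: early stop 0.5888, type I error 0.0415, power 0.807. This matches the stated 0.589 and 80% and stays within 0.05.
- r1 = 2 (the rule as literally written, fewer than 3 of 18), r = 11: early stop 0.346, type I error 0.0439, power 0.826.

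The figures below use stop at ≤3/18 and success at ≥12/40. Both boundaries are inferred. The mismatch between the written stage 1 rule and 0.589 is a separate matter.

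**Step 2: what each handling does to the 6-month result.** Let e be the fraction of treated patients who are clinical failures without objective progression, and let the true success rate among all treated patients be 18%.

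- *Kept in the denominator as non-successes:* the rate stays 0.18 and type I error stays 0.0415. Nothing changes.
- *Excluded, not replaced, 12-success boundary kept:* the number of successes among the 40 enrolled is the same, so the false-positive rate does not exceed 0.0415. The reported proportion still rises. With e = 10%, expected successes are 0.18 × 40 = 7.2, and 7.2/36 = 20.0%.
- *Excluded and replaced until 40 remain:* the success rate among those counted is 0.18/(1 − e), and the full boundary is applied to the enriched sample.
- *Censored:* the rate is biased upward. The documents give nothing from which to size this.

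**Step 3: size under exclusion with replacement.** The values of e are assumptions; the documents give no figure.

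| e (assumed) | 0.18/(1 − e) | P(success), stop ≤3/18 | P(success), stop ≤2/18 |
|---|---|---|---|
| 0 | 18.0% | 0.0415 | 0.044 |
| 5% | 18.9% | 0.058 | 0.062 |
| 10% | 20.0% | 0.082 | 0.086 |
| 15% | 21.2% | 0.115 | 0.121 |
| 20% | 22.5% | 0.160 | 0.169 |

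Every row with e > 0 exceeds the stated 0.05, and the choice of stage 1 boundary makes little difference.

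**Step 4: is there a route to replacement in the plan?** Yes, a partial one. A patient who declines before week 9 will often have missed doses, and 3.3.2 then replaces that patient whatever the reason. The route does not reach patients who decline after week 9 or who had taken enough drug, so e in Step 3 should be read as the fraction actually replaced. Section 12.1 also makes evaluability depend on re-evaluated disease, with an early-failure exception for objective progression only. That definition is for objective response, not PFS.

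**The case against.** The strongest case on the other side is that this is a gap in wording with little effect on the decision. Most of its points stand.

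- A reader might infer that 14.1.1 makes clinical progression alone an event and so flatly contradicts 12.4 and 11.4. The text does not support that. It joins clinical assessment and RECIST with *and*, and requires progression to be documented. Clinical assessment also has a place inside the protocol's own RECIST section, through caliper measurement and the physician's view of non-target lesions. A coherent reading exists; the plan simply does not state it.
- Section 11.4 is a rule about removal from study, and 12.4 assigns a reporting label. Neither says that such a patient is censored or not evaluable for PFS. Section 12.4 also asks for objective progression to be sought after treatment stops, and death is a PFS event in both definitions.
- Under 14.2 a patient without a 6-month scan has not been shown to have stable disease. While that patient stays in the denominator, the natural reading is a non-success.
- A reader might also infer that the conflict between sections by itself pushes type I error to 0.16. It does not. That figure needs 20% of patients to be both excluded and replaced, and the only Phase II replacement rule is triggered by doses taken, not by how progression is defined.

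The objection does not remove two things. The request in 12.4 to document progression later has no scheduled scan behind it. And no section says that clinical failures remain in the denominator, while 3.3.2 can take some of them out.

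**Conclusion.** The point holds as an unresolved specification of the primary endpoint, not as an irreconcilable contradiction. The role of clinical progression in the 6-month count is not stated, and 14.1.1, 12.4 and 14.2 must be reconciled.

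The consequence is conditional. It is nil if clinical failures are retained as non-successes, and an upward bias if they are censored or dropped and replaced. The range 0.058 to 0.160, against 0.0415, is an illustration. It rests on assumed fractions of 5% to 20%, on full replacement up to 40, on inferred boundaries, and on a null of 18% that applies to all treated patients. The documents do not give the source of the 18% or the event definition behind it. The change is worth making because the decision is a single-arm count and the repair is a matter of wording.

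**What to change.** Write one definition of 6-month success into 14.1.1 and 14.2, and refer to it from 12.4 and 12.5:

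- **Success:** alive, with a 6-month assessment scan showing no RECIST 1.1 progression. Name the scan that serves; on the 9-week schedule the third falls at 3 × 9 = 27 weeks, with a one-week window.
- **Non-success:** death, RECIST progression, symptomatic deterioration, or no qualifying scan.
- **Denominator:** all treated patients. Align 3.3.2 so that a replaced patient still counts in the primary analysis. Because replacement can then take the number treated above 40, state how the stage 1 and final boundaries apply in that case.
- **Sensitivity analysis:** PFS with RECIST progression or death as the only events, with its censoring rule stated.

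The cost is wording in 14.1.1, 14.2 and 3.3.2. The observed 6-month rate may come out slightly lower, since patients without a scan count against the treatment.
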